8.1. Overview

We will conduct a Stage 1 pilot feasibility study at McLean Hospital to develop a combination of medication protocol to treat cannabis dependence in subjects with schizophrenia, schizoaffective, or any Axis I disorder. In a randomized, double-blind, placebo-controlled trial, 18 cannabis-dependent male an female subjects ages 18-45 with an Axis 1 psychiatric disorder will receive medical management (MM) over a 10-week period, with half receiving treatment with the combination of dronabinol and clonidine and half receiving placebo. Subjects will receive either the combination of dronabinol 5 mg by mouth three times daily and clonidine 0.1 mg my mouth twice daily or placebo in addition to MM over a 10-week treatment period. A follow-up visit after treatment at week 14 will evaluate the durability of treatment effects on drug use and psychosocial outcomes. Primary outcomes will include self-report of cannabis smoking and results of quantitative urine drug screens for cannabis. We also will assess cannabis withdrawal symptoms, including mood and craving. Mixed models ANOVA will be used to analyze the data.

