		Week	1	Weeks 5,10	
Diagnostic Assessment					
Structured Clinical Interview	X B1				
for DSM-IV ^a	ABI				
Drug and Alcohol Assessment					
2. Quantitative Urine Toxicological	XB1,B2	X^{b}	X	X	X
Analysis ^b	•				
3. Addiction Severity Index	XB2		X	X	X
4. Drug and Alcohol Use Questionnaire	XB1				
5. Weekly Drug and Alcohol Use Inventory	XB1,B2	X	X	X	X
6. Marijuana Goals Questionnaire	XB1				
7. Marijuana Craving Questionnaire	XB1,B2	X	X	X	X
8. Marijuana Withdrawal Checklist	XB1,B2	X	X	X	X
Mood and Impulsivity Assessment					
9. Quick Inventory of Depressive	TID1 DA			***	***
Symptomatology	XB1,B2			X	X
10. Barratt Impulsiveness Scale	XB1,B2			X	X
11. Beck Anxiety Inventory	XB1,B2			X	X
Medical & Safety Assessment	VD1				37
12. Physical examination 13. ECG	XB1 XB1				X
	XB1,B2	X	X	X	X X
14. Urine pregnancy test	AD1,D2	Λ	Λ	Λ	Λ
15. Vital Signs ^c	XB1,B2	X	X	X	X
16. Positive and Negative Syndrome Scale	XB1,B2				
17. Behavioral Activity Rating Scale	XB1		X		
18. Laboratory tests ^d	XB1			X	X
19. Adverse Events & Side Effects	XB1,B2	X	X	X	X
20. Columbia Suicide Severity	XB1	X	X	X	X
21. Marijuana Perceptions of Risk and	XB1			X	X
Experiences Questionnaire (MPRE)					
Rating Scale					

^aFull SCID at baseline

8.2.1.f. Clinical Emergencies. If a subject is intoxicated, the subject will be evaluated medically, sent home in a taxi when safe, and the appointment re-scheduled. If a subject experiences a problem that requires clinical intervention during the course of the study (e.g., mania, suicidal ideation, or dangerous intoxication), we will evaluate the situation medically, make an appropriate recommendation, and help the subject to implement this plan. This could involve hospitalization at McLean, referral to the hospital's outpatient program, or other medical or psychiatric treatment, as clinically appropriate.

Partners Human Subjects Research Application Form

^bTwice a week during treatment

^cVital Signs include pulse and blood pressure (sitting and standing)

^dTests include urinalysis, liver function tests, electrolytes, complete blood count, & blood chemistries B1= Baseline 1 (screening visit)

B2=Baseline 2 (baseline 2 visit post screen for subjects who qualify for participation before treatment begins)

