Analyses of secondary substance use outcomes will focus on the number of days of cannabis use and of any substance use (and conversely, days of abstinence) during treatment and post-treatment follow-up. In addition, we will also examine the ASI Drug and Alcohol composite scores. Frequency of days of cannabis use (and any substance use and days of abstinence) will be analyzed via a log-linear (or Poisson) regression model, controlling for pre-treatment frequency of days of cannabis use. Although loglinear regression methods are considered appropriate for the analysis of count or frequency data, in many biomedical applications, count data have variability that far exceeds that predicted by the Poisson distribution; we expect that days of cannabis use (and any substance use and days of abstinence) will not be an exception. Linear mixed effects models will be used to examine the effect of treatment group on changes in the ASI Drug and Alcohol composite scores during treatment and post-treatment follow-up assessments (as determined by the group-by-time interaction in the linear mixed effects regression models). The linear mixed effects model will include random intercepts and slopes to appropriately account for correlation among repeated measures and heterogeneity of variance over time; the model will be fit using PROC MIXED in SAS.

In secondary analyses of mood outcomes, mood episodes will be assessed during treatment and post-treatment follow-up, using the QIDS-SR, , BAI, and BIS-11; ; changes in risk of mood episodes during treatment and post-treatment follow-up assessments will be analyzed via a logistic regression model (similar to the logistic model above) that will be fit using the GEE approach (as implemented in PROC GENMOD in SAS) to account for correlation among repeated binary outcomes on the same individual. To examine the effect of dronabinol and clonidine on changes in risk for mood episodes during treatment and post-treatment follow-up, the logistic regression model will include the effects of treatment condition and the baseline measure of the outcome.

For studies involving treatment or diagnosis, provide information about standard of care at McLean (e.g., BWH, MGH) and indicate how the study procedures differ from standard care. Provide information on available alternative treatments, procedures, or methods of diagnosis.

The standard of care for cannabis dependence is psychotherapy; our treatment centers upon a medication.

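### The mood model in 8.9 is meant to examine risk during treatment and after it, but lists only treatment and baseline; fitted as listed, it gives one odds ratio averaged over weeks 5, 10 and 14

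*Combined protocol and SAP*

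**What the plan says.** The mood paragraph of section 8.9 (Statistical Analysis) states that "changes in risk of mood episodes during treatment and post-treatment follow-up assessments will be analyzed via a logistic regression model". The method is GEE, used "to account for correlation among repeated binary outcomes on the same individual". The aim is then restated ("To examine the effect of dronabinol and clonidine on changes in risk for mood episodes during treatment and post-treatment follow-up") and the terms follow: "the logistic regression model will include the effects of treatment condition and the baseline measure of the outcome".

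The model is described as "similar to the logistic model above", but 8.9 contains no earlier logistic model. The paragraph on cannabis use names GEE without a link function or covariates.

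Table 1 places the three mood scales (QIDS-SR, BIS-11, BAI) at baseline, weeks 5 and 10, and week 14. Section 8.2.1.e sets treatment at 10 weeks. For the ASI scores, the preceding paragraph of 8.9 judges change over the same two phases "as determined by the group-by-time interaction in the linear mixed effects regression models".

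**The concern.** The stated aim covers two phases, and the listed terms allow one answer. A treatment coefficient adjusted for baseline is a legitimate average effect on post-baseline risk, but it does not say whether the effect arose on drug, after drug, or in both phases.

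The split matters because the protocol's section on foreseeable risks lists depression and anxiety among possible side effects. A mood effect tied to drug exposure is therefore one that the protocol itself anticipates. If such an effect ends with treatment, the average understates it. A null average would not show that there was no on-drug effect, and a positive one would not show that an effect lasted.

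**Working it through.** The documents give no power, effect size or episode rate for mood, so there is no planned figure to reproduce. The check is of structure first, then of size under stated assumptions.

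**1. Visits.** Post-baseline mood visits are weeks 5, 10 and 14 (Table 1). Treatment ends at week 10 (8.2.1.e), and 14 − 10 = 4. So two visits are on drug and one is four weeks after it.

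**2. Model as listed.** For subject i at visit j: logit P(Y_ij = 1) = b0 + b1·treatment_i + b2·baseline_i. The coefficient b1 carries no visit index, so the fit returns one odds ratio. The ASI model in the same section does have a group-by-time term.

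**3. Size of the dilution.** Assumptions: constant placebo risk p0 of 20-50%, on-drug odds ratio θ at weeks 5 and 10, equal weight per visit, no adjustment for baseline.

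- On-drug risk: p_on = θ·o / (1 + θ·o), with o = p0 / (1 − p0).
- Mean active risk: m = (2·p_on + p14) / 3.
- Pooled odds ratio: [m / (1 − m)] / o.

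With no effect at week 14 (p14 = p0):

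- θ = 2, p0 = 0.5: p_on = 0.667; m = (1.333 + 0.5)/3 = 0.611; pooled OR = 1.57.
- θ = 2, p0 = 0.2: p_on = 0.333; m = (0.667 + 0.2)/3 = 0.289; pooled OR = 0.406/0.25 = 1.63.
- θ = 0.5, p0 = 0.5: p_on = 0.333; m = 0.389; pooled OR = 0.64.
- θ = 0.5, p0 = 0.2: p_on = 0.111; m = 0.141; pooled OR = 0.164/0.25 = 0.66.

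| On-drug OR | Pooled OR, no effect at week 14 | Share of log OR kept | Pooled OR, equal and opposite log OR at week 14 |
|---|---|---|---|
| 2 | 1.57-1.63 | 65-70% | 1.25-1.40 |
| 3 | 2.00-2.18 | 63-71% | 1.40-1.81 |
| 0.5 | 0.64-0.66 | 61-65% | 0.80-0.91 |
| 1/3 | 0.50-0.53 | 57-63% | 0.71-0.96 |

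This distortion does not depend on sample size.

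**4. Power.** Simulation of 20,000 trials per row: 9 v 9 (section 8.1: 18 subjects, half per arm), no dropout, logistic model with subject-effect SD 1, average risks as shown, two-sided 5%. Arms are compared by a t test (16 df) on subject means over three visits or over weeks 5 and 10.

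| Placebo v active risk on drug | Week 14, active arm | Three-visit average | Weeks 5 and 10 |
|---|---|---|---|
| 50% v 33% | 50% | 11% | 15% |
| 40% v 15% | 40% | 20% | 35% |
| 50% v 10% | 50% | 44% | 72% |
| 50% v 10% | 80% (rebound) | 22% | 72% |
| 50% v 10% | 10% (persists) | 82% | 72% |
| 50% v 50% | 50% | 5% | 5% |

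Where the effect is gone at week 14, the losses are 4, 15 and 28 points. Where it persists unchanged, the average gains 10.

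**5. Sparse data.** At 10% active risk, about 17% of simulated trials have no on-drug event in the active arm, so an ordinary on-drug odds ratio is not finite. If that risk persists, about 38% of trials have an arm with all or no events at week 14. The week-14 contrast alone has about 50% power at 50% v 10%, and about 11% at 50% v 33%.

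**The case against.** - **Terms listed are not terms excluded.** The text says what the model will include; it does not say that nothing else enters. With the cross-referenced model absent, the full specification is unknown. This stands: a reader might infer that the plan definitely tests a single average, but the documents support only that no time term is listed and that the pointer leads nowhere.
- **The two phases may only describe which visits enter the model.** That reading is possible. But near-identical wording for the ASI is answered with a group-by-time term, and the mood sentence speaks of changes in risk.
- **Durability.** A reader might infer that section 8.1 promises a durability result for mood: "A follow-up visit after treatment at week 14 will evaluate the durability of treatment effects on drug use and psychosocial outcomes". That section names mood with withdrawal symptoms and does not say that it counts as psychosocial, so the inference is not secure. The point rests on the aim in 8.9.
- **Large power losses.** The 28-point loss needs an odds ratio of 1/9, and a 50-point loss needs a rebound to 80% as well. The documents support neither as a headline. The simulation is also an unadjusted stand-in for the GEE and ignores the 20% dropout allowed for in 8.2, which would lower power throughout.
- **Limited consequence.** This is a secondary analysis in an 18-subject pilot. A reader might infer that mood harm would go unseen. It would not: adverse events and the C-SSRS are scheduled through treatment (Table 1), and suicide risk is assessed at each medical management visit (8.2.1.a).

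**Conclusion.** The point holds as a mismatch between a stated aim and the terms listed to meet it. It goes beyond missing detail, because the model fitted as listed cannot answer the question that 8.9 sets.

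The effect on the estimate is moderate. A purely on-drug effect keeps about 57-71% of its log odds ratio under the assumed placebo risks of 20-50%, so it is diluted, not erased. An equal reversal at week 14 leaves about 3-54%. The exact weights depend on the working correlation and on missing visits, neither of which is specified for this model.

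Power is a lesser matter, since it is low at plausible effects whichever contrast is used. The pooled average is valid and is the stronger test if the effect persists, so there is no case for discarding it. The change is worth making, but the trial's primary conclusions do not depend on it.

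**What to change.** In 8.9, add to the mood model a period term (weeks 5 and 10; week 14) and treatment-by-period, in line with the ASI model. Report the treatment odds ratio with its confidence interval for each period, beside the pooled average. Replace the reference to a model above with the full list of terms and the working correlation.

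State in advance what will be reported if an arm has no events or only events in a period: risk differences, or a small-sample (penalised) fit.

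The cost is one or two sentences and no new data or visits. The downsides are two further estimates that will be imprecise at 9 per arm, a weak week-14 contrast, and the risk of empty cells. A separate gap must be closed before any version can be fitted: 8.9 does not say how the three scales define a binary mood episode.

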Subjects who experience uncomfortable side effects (e.g., drowsiness or vertigo) may have their dose lowered from 2 capsules three times a day to 2 capsules twice daily by eliminating the middle dose of the day; a subject receiving active medication, for example, could then have a dronabinol dose reduction to 10 mg of dronabinol daily. If this leads to fewer side effects, the study physician will ask if the subject is willing to try the full dose again. If not, or if the subject tries the full dose again and is unable to tolerate it, the subject will be maintained on the lower dose. If a subject cannot tolerate 2 capsules twice per day, the medication will be discontinued, and the subject will be tapered off of the Clonidine, but the subject will continue to be followed for research visits. Similarly, we will monitor for potential cardiovascular side effects resulting from clonidine pharmacotherapy. At each medical management visit, we will assess vital signs and ask the subject about symptoms of orthostatic hypotension, such as dizziness when rising to stand from a seated position, blurry vision, or weakness. If subjects describe these symptoms without meeting exclusionary blood pressure criteria, we will hold the third set of capsules to see if this leads to fewer side effects, the study physician will ask if the subject is willing to try the full dose again. If not, or if the subject tries the full dose again and is unable to tolerate

Partners Human Subjects Research Application Form

Version Date: July 26, 2016

it, the subject will be maintained on the lower dose. If a subject cannot tolerate 2 capsules twice per day, the medication will be discontinued, but the subject will continue to be followed for research visits.

8.3.2. Medical Management Visits.

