Describe how risks to subjects are minimized, for example, by using procedures which are consistent with sound research design and which do not unnecessarily expose subjects to risk or by using procedures already being performed on the subject for diagnostic or treatment purposes.

Partners Human Subjects Research Application Form Version Date: July 26, 2016

Care will be taken to minimize risk. In addition to carefully screening prior to enrollment, we have scheduled regular laboratory visits during which we will carefully monitor response to medication or placebo with respect to side effects and changes in mood.

Describe explicitly the methods for ensuring the safety of subjects. Provide objective criteria for removing a subject from the study, for example, objective criteria for worsening disease/lack of improvement and/or unacceptable adverse events. The inclusion of objective drop criteria is especially important in studies designed with placebo control groups.

8.3.1.b. Safety Monitoring.

In order to monitor potential side effects from the initial dose of dronabinol, subjects will be observed at the laboratory facility for 4 hours following the following the first dose of the day in week 1. Subjects will come into the Behavioral Psychopharmacology Research Laboratory for monitoring by a research assistant and a study physician. This observation period is follows the SAMHSA guidelines for induction of buprenorphine, another agonist pharmacotherapy (CSAT 2004). Subjects will remain in the natural settings laboratory for a minimum of 2 hours and a maximum of 6 hours while having vital signs taken every 30 minutes. Subjects will be allowed to leave the facility by cab after being cleared by a study physician. Subjects will be allowed to leave the facility if they have 1) pulse rate greater than or equal to 50 beats per minute or less than or equal to 135 beats per minute; 2) blood pressure less than or equal to 140/90 and greater than or equal to 90/50; and 3) Behavioral Activity Rating Scale (BARS) score of less than 6. If pulse is decreasing, blood pressure is increasing, or BARS is increasing at the 2-hour assessment, the subject will remain an addition 30 minutes until the trend for these parameters is in the correct direction and the subject meets criteria for medical clearance.

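### The pulse limits for leaving after the first monitored dose are joined by 'or', so every pulse meets them and the upper limit of 135 bpm does not bind

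*Combined protocol and SAP*

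**What the plan says.** Section 8.3.1.b describes the observation period after the first dose in week 1. Subjects stay in the laboratory "while having vital signs taken every 30 minutes". On departure it says: "Subjects will be allowed to leave the facility by cab after being cleared by a study physician". It then lists three numbered criteria, all of which must be met:

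1. Pulse: "pulse rate greater than or equal to 50 beats per minute or less than or equal to 135 beats per minute".
2. Blood pressure: "blood pressure less than or equal to 140/90 and greater than or equal to 90/50".
3. A Behavioral Activity Rating Scale (BARS) score below 6.

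A trend rule follows. "If pulse is decreasing, blood pressure is increasing, or BARS is increasing at the 2-hour assessment", the subject stays a further 30 minutes, until the trend is in the right direction and the clearance criteria are met.

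The 50 to 135 range is not restated anywhere else. The other numeric pulse limits are the bradycardia limits of 50 bpm or lower, in the Stopping Criteria paragraph and in Section 9.4, item 9. They concern screening and pre-dose assessment.

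**The concern.** Two limits joined by 'or' describe a range only if both are meant to bind, and 'or' does not make them bind. Here the lower limit lies below the upper one, so the two conditions together cover every possible pulse.

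This is an operative threshold for sending a subject home by cab after a first dose of two drugs that act on the cardiovascular system. The upper limit matters most. The Foreseeable Risks and Discomforts section lists a fast heart rate and fainting among possible side effects, in a sentence that opens with dronabinol although it then names nabilone. The figure of 135 bpm is the protocol's only numeric guard against a fast pulse.

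**Working it through.** The plan gives no figure to reproduce here, so the check is one of logic.

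**Step 1: the pulse item.** Write *p* for the pulse in bpm.

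| Pulse | *p* ≥ 50 | *p* ≤ 135 | As written ('or') | With 'and' |
|---|---|---|---|---|
| below 50 | false | true | met | not met |
| 50 to 135 | true | true | met | met |
| above 135 | true | false | met | not met |

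The three rows exhaust all values. As written, no pulse fails. With 'and', only 50 to 135 passes.

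**Step 2: the neighbouring item as a guide to intent.** The blood pressure item joins its limits with 'and', and it works at both ends: 160/100 fails the upper limit, 85/45 fails the lower, and 120/80 passes. The pulse item has the same form apart from the joining word. Printing two limits would also serve no purpose if neither were meant to exclude anyone.

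**Step 3: a worked case.** Take a pulse of 150 bpm and rising, blood pressure steady at 120/80, and BARS steady at 4.

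- Pulse as written: 150 ≥ 50 is true, so the item is met. With 'and': 150 ≤ 135 is false, so it is not met.
- Blood pressure: 120 ≤ 140, 80 ≤ 90, 120 ≥ 90 and 80 ≥ 50, so it is met.
- BARS: 4 < 6, so it is met.
- Trend rule: the pulse is not decreasing, blood pressure is not increasing and BARS is not increasing, so there is no hold.

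As written, this subject meets every numeric condition for leaving. With 'and', the subject stays.

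**Step 4: whether another numeric rule supplies the missing limit.** The trend rule does not, because a rising pulse is not among its triggers. The bradycardia limits do not, because they address a slow pulse. Section 8.3.1.b gives no separate pulse figure for the physician's clearance.

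**The case against.** The strongest reply is that this is a slip of wording and that nobody would apply it literally. The figures 50 and 135 are on the page, the next item uses 'and', and a physician would probably read the pulse item as a range. The decision is also led by a physician and is not made by formula. A research assistant and a study physician monitor the session, vital signs are taken every half hour and there is a minimum stay. Section 8.3 adds ACLS-trained physicians and a crash cart, and the Data and Safety Monitoring section promises a low threshold for further medical workup.

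Most of this stands. It makes the intent clear and limits the practical risk. It does not make the limit operate, because these safeguards rest on clinical judgement and none restores a numeric ceiling on pulse. A written safety criterion should not depend on its readers silently correcting it.

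A reader might go further and infer that the protocol would send home subjects with unsafe pulse rates, or that no limit was intended. The documents support neither inference. Clearance by a physician is required in every case, and the two printed limits show that a range was meant.

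**Conclusion.** The point holds as an error in an operative safety rule. As written, the pulse criterion excludes nobody, and the only upper pulse limit in the protocol is lost. That conclusion follows from the wording alone. The fast-pulse case in the working also assumes that blood pressure and BARS are acceptable and steady. The number of subjects who might be affected cannot be derived from the documents, and no sample size, endpoint or analysis is touched. The correction is worth making because the error is certain and the rule protects subjects.

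Two wider readings are tempting but not supported:

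- **A slow, steady pulse.** A reader might infer that such a subject leaves just as freely as one with a fast pulse. The lower limit is indeed inoperative in the pulse item. However, a subject at or below 50 bpm before dosing already meets the bradycardia limits, and one who started above 50 must have fallen to get there. Section 8.3.1.b does not say whether a decreasing pulse is judged against the pre-dose value or the last reading. If it is judged against the pre-dose value, the trend rule would hold that subject.
- **Dizziness on standing.** A reader might also see a conflict between Section 8.3.1.c, which says "If subjects describe these symptoms without meeting exclusionary blood pressure criteria, we will hold the third set of capsules", and the Stopping Criteria, which list symptoms due to low blood pressure as a reason to stop clonidine. The exclusionary criteria can be read as Section 9.4, item 9, which already includes such symptoms. On that reading, holding and retrying applies only to symptoms not attributed to low blood pressure, and the two sections agree.

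**What to change.** In Section 8.3.1.b, change 'or' to 'and' in the pulse item, so that a subject may leave only with a pulse of at least 50 bpm and at most 135 bpm. This matches the form of the blood pressure item. The cost is one word in an amendment, with no added visits, procedures or subjects and no change to the analysis.
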